3.2 Analysis Sets

3.2.1 Full Analysis Set

The Full Analysis Set (FAS) will serve as the primary population for the analysis of tumor response and other efficacy-related endpoints in the Phase 2 portion of the study. The FAS is a subset of all enrolled patients, with patients excluded for the following reasons:

- Failure to receive at least one dose of entinostat and pembrolizumab
- Lack of baseline data for those analyses that require baseline data

3.2.2 Per-Protocol Analysis Set

The Per-Protocol Analysis Set is a subset of the FAS. The Per-Protocol Analysis Set consists of all patients who do not violate the terms of the protocol in a way that would majorly impact the study outcome. All decisions to exclude patients for the Per-Protocol Analysis Set will be made prior to the data freeze for the primary analysis.

3.2.3 Evaluable Analysis Set

The Evaluable Analysis Set is a subset of the FAS. The Evaluable Analysis Set is defined as patients who had week 6 assessment or were removed from study for progression of disease (or suspected progression) or for adverse event that was attributed to study drug. Patients who were excluded from Evaluable Analysis Set included those who discontinued due to adverse events that were not related to study drug or withdrew consent from treatment or study before the Week 6 scan assessment.

3.2.4 Safety Analysis Set

Without otherwise specified, the Safety Analysis Set will be used for the analysis of safety data in both the Phase 1b and Phase 2 portions of the study. The Safety Analysis Set will include all patients who received at least one dose of either study drug, entinostat, or pembrolizumab. At least one laboratory or vital sign measurement obtained, subsequent to at least one dose of study treatment, is required for inclusion in the analysis of a safety specific parameter. To assess change from baseline, a baseline measurement is also required.

3.2.5 Pharmacokinetic Analysis Set

Patients will be evaluable for the primary PK analysis if they receive the reference agent administered with and without the other agent. Additionally, patients must have sufficient plasma concentration-time data from each treatment period in order to provide for meaningful assessment of the PK parameters (e.g., AUC and C_{max}). The PK Analysis Set will include all patients who have evaluable plasma concentration-time

data for each treatment period, and for whom one or more of the designated PK parameters can be determined.

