**Study Design:**

Study SNDX-275-0601 is an open-label, Phase 1b/2 study evaluating the combination of entinostat plus pembrolizumab in patients with advanced metastatic or recurrent NSCLC, melanoma or mismatch repair-proficient colorectal cancer. The study has 2 phases, a Dose Escalation/Confirmation Phase (Phase 1b) and an Expansion Phase (Phase 2), with the Expansion Phase utilizing a Simon 2-stage design (Simon 1989) for cohorts 1 and 4. For cohorts 2 and 3, the single proportion binomial test statistic is used to test for statistical significance. An additional cohort (Entinostat Monotherapy Immune Correlate [EMIC] Cohort) evaluating single agent entinostat followed by the combination will also be evaluated in patients with NSCLC in the Phase 2 expansion phase.

Regardless of phase, patients will be screened for study eligibility within 21 days before enrollment into the study. Patients who are determined to be eligible, based on screening assessments, will be enrolled into the study within 3 days of starting study treatment. With the exception of those in the EMIC cohort, patients will receive entinostat in combination with pembrolizumab on Cycle 1, Day 1 (C1D1), within 3 days from enrolling into the study.

A total of 15 patients will be enrolled in an EMIC Cohort. EMIC patients will be enrolled in the study within 3 days of starting study treatment on Day -14 (initiation of entinostat monotherapy) and will participate in a 2-week entinostat monotherapy period. The purpose of this 14-day lead-in phase is to obtain pre-and post-entinostat monotherapy correlative data in blood and tissue. After completion of the 2-week entinostat monotherapy period, patients in the EMIC Cohort will start entinostat in combination with pembrolizumab on C1D1. Patients in the EMIC Cohort will receive entinostat beginning at 5mg weekly for the monotherapy period, and then will receive entinostat in combination with pembrolizumab at the RP2D as identified in the Phase 1b Dose Escalation/Confirmation portion of the study.

A cycle is 21 days in length. During treatment, patients will attend study center visits and have study evaluations performed on C1D1, C1D8, and C1D15; D1 and D15 of C2; and on D1 of each cycle thereafter.

Fresh tumor tissue samples will be collected during the study as follows:

- During **screening** from **all** patients on a **mandatory** basis.

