#### Expansion Phase

In the Expansion Phase of the study, the safety and preliminary antitumor activity of entinostat when administered at the RP2D with pembrolizumab will be explored in up to 4 cohorts of adult solid tumors as previously defined. Up to 252 patients are planned to be enrolled among the 4 cohorts. Patients will be enrolled in each cohort according to a single-arm study design with ORR, as determined by irRECIST, as the primary endpoint. The Expansion Phase will be carried out in 2 stages so that enrollment for 1 or more of the cohorts evaluated can terminate early in the event the antitumor activity of the combination regimen is not sufficient. The decision to terminate or continue enrollment for each cohort will be made independently of the other. The number of patients evaluated in each stage and the minimum number of responders needed to continue to the next stage, as described for cohort 1, was determined based on the optimum version of Simon's 2-stage design (Simon 1989), with 80% power and 1-sided significance level of 10%. For cohort 4, the number of patients evaluated in each stage and the minimum number of responders needed to continue to the next stage was determined based on optimum version of Simon's 2-stage design, with 90% power and 1-sided significance level of 5%. For cohorts 2 and 3, the number of responders needed to declare the study a success was based on single proportion binomial test with 90% power and 1-sided significance level of 5%. Note that the protocol may be amended to allow for enrollment of additional or different cohorts, for example, patients with PD-L1-positive NSCLC, based on emerging data during study conduct.

Syndax will conduct one administrative analysis when at least 60% (42 out of 70 patients in cohort 2, 31 out of 52 patients in cohort 3) of patient information have accrued in cohorts 2 and 3 for decision making for late phase development planning. This administrative look will not lead to stopping of the study. Nonetheless, 0.01 alpha is being allocated to spend for the first administrative look and leaving 0.04 alpha for the final analysis.

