3.3.2 Pharmacokinetic Variables

The following PK parameters for the plasma concentrations of entinostat or pembrolizumab will be calculated via non-compartmental methods and summarized, where applicable, using the WinNonlin™ software package (WinNonlin™ Phoenix, Version 6.3, Pharsight Corporation, Mountain View, CA).

Pharmacokinetic variables include:

- C_{max} , maximum plasma concentration
- T_{max} , time at which maximum plasma concentration was observed
- AUC_{0-t} , area under the plasma concentration-time curve from time zero to the last measurable concentration
- AUC_{0-inf} , area under the plasma concentration-time curve from time zero extrapolated to infinity
- $t_{1/2}$, elimination half-life
- λ_z , terminal elimination rate constant

All measurable plasma concentrations will be used for the analysis. For concentration values reported as no Results/not Reportable (NR), values will be treated as missing.

Values below the quantifiable limit (BQL) that occur prior to the first measurable concentration will be treated as zero. All other BQL values will be treated as missing. The mean plasma concentration over time by treatment and the individual subject plasma concentration versus time data will be plotted. Nominal times will be used for plotting the mean plasma concentrations over time by treatment. Actual sampling times will be used for the individual figures and for the non-compartmental analysis.

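### The SAP's evaluability rule for the primary PK analysis needs single-agent PK data that no cohort is scheduled to provide, and several listed PK parameters cannot be obtained from the sampling schedule

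*SAP*

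**What the plan says.** SAP 3.2.5 has three sentences. The first sets a condition for the primary PK analysis: "Patients will be evaluable for the primary PK analysis if they receive the reference agent administered with and without the other agent". The second adds that "patients must have sufficient plasma concentration-time data from each treatment period in order to provide for meaningful assessment of the PK parameters", giving AUC and Cmax as examples. The third defines set membership. It begins "The PK Analysis Set will include all patients who have evaluable plasma concentration-time", asks for such data in each treatment period, and adds that at least one designated parameter must be determinable. It does not repeat the with-and-without condition. The visible text of the SAP does not define the reference agent or a treatment period.

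SAP 3.3.2 lists Cmax, Tmax, AUC0-t, AUC0-inf, half-life and lambda_z for entinostat or pembrolizumab. These "will be calculated via non-compartmental methods and summarized, where applicable". AUC0-t is the "area under the plasma concentration-time curve from time zero to the last measurable concentration". SAP 6.1 plans a parameter table for each drug (14.2.2.1 and 14.2.2.2), by title only, and two concentration tables (14.2.1.1 and 14.2.1.2). All four titles carry the tag (PK).

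SAP 3.11 and protocol 12.4.8 plan something different: population PK for entinostat, with details left to a separate plan. SAP 3.11 adds descriptive summaries for pembrolizumab.

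**The concern.** The first two sentences of 3.2.5 are drug-interaction wording: they suit a design in which each patient is sampled on one drug alone and again on both. This trial schedules no such sampling. A programmer who applies them has almost nobody to analyse. One who applies only the third sentence may include most sampled patients. The parameter list raises a second problem, because it assumes concentration profiles that the schedule does not collect. At stake is whether the PK tables have a defined population and interpretable contents.

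**Working it through.** The documents give no sample size or precision target for PK, so there is no figure to reproduce. The check counts scheduled samples and asks what each set can support.

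**1. Samples in a planned single-agent period**

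- Cohorts 1-4 have at most 46 + 70 + 52 + 84 = 252 patients (protocol 12.1.2). They and the Phase 1b patients start both drugs on C1D1, so they have no single-agent period: 0 samples.
- EMIC: "A total of 15 patients will be enrolled in an EMIC Cohort". Entinostat is given alone from D-14 to D-1 (protocol 8.1.1). Protocol 5.1 sends PK sampling to the schedule of events, and protocol 9 names Table 1-2 as the EMIC schedule. Table 1-1 has PK rows and footnotes 17 and 18; Table 1-2 has neither. Scheduled samples: 0.
- Protocol 9.5 lists time points without excepting EMIC. If it applied, the C1D1 pre-dose sample would be one entinostat-alone concentration in at most 15 patients. One point gives no AUC and no meaningful Cmax.
- No cohort has a planned pembrolizumab-alone period. Protocol 8.3 lets a patient stop one drug and continue the other, but that is unplanned and its frequency is not given.

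**2. Entinostat parameters**

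Samples (protocol 9.5.1, SAP 2.3.7): C1D1 pre-dose; C1D1 at 2-4 h; C1D8 any time post-dose; C1D15 any time post-dose; C2D1 pre-dose. Doses fall at 0, 168 and 336 h, so the three weekly intervals hold 1, 1 and 2 post-dose samples. Protocol 4.3.1 gives a half-life of 40 to 120 h.

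- *Carry-over.* The fraction of a dose's concentration left at 168 h is 2^(-168/half-life): 5.4% at 40 h and 37.9% at 120 h. Later samples therefore mix doses.
- *Terminal slope.* I assume the usual requirement of at least three terminal points, which the documents do not state. No interval reaches it. The third interval allows a line through two points with no check of fit. A simulation with an assumed 20% error per concentration gives these 5th-95th percentiles: for a true half-life of 40 h, 34-48 h if the C1D15 sample is taken at 2 h; for 120 h, 80-231 h if taken at 2 h and 65-689 h if taken at 72 h. AUC0-inf needs the same slope.
- *AUC0-t.* The SAP does not say where the profile ends.
  - If it ends at the C1D1 2-4 h sample, the share of AUC0-inf is 1 - 2^(-t/half-life), assuming mono-exponential decline. At t = 2 h this is 1.15% (120 h) to 3.4% (40 h). At t = 4 h it is 2.3% (120 h) to 6.7% (40 h).
  - If it runs from 0 to 504 h across three doses, I assume instant absorption and a linear trapezoid through zero at pre-dose and the four later samples. With the any-time samples 1-24 h after dosing, estimated/true area is 1.92-2.56 (40 h), 1.46-1.69 (80 h) and 1.32-1.47 (120 h). If they may fall up to 160 h after dosing, the overall range is 0.84-2.56.

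**3. Pembrolizumab parameters**

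Pre-dose samples over 35 cycles (protocol 9.5.2, 8.3): C1, 2, 4, 6, 8, 12, 16, 20, 24, 28 and 32, which is 11, of which 10 follow a dose. There are 34 dose-to-dose intervals: 10 hold one sample, always a trough, and 34 - 10 = 24 hold none. One further sample is taken 30 days after the last dose. No sample is timed at the peak, and no interval has the two points needed for a slope.

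**The case against.** The strongest reply is that the tables do not rest on the first sentence. Titles in SAP 6.1 are tagged by analysis set, and all four PK titles say (PK), which points to the membership sentence. No visible table or section uses the term primary PK analysis. The membership sentence asks only that one parameter be determinable, so it allows for incomplete profiles. This largely stands: a reader might infer that the PK tables would be empty, and the documents do not support that. What remains is an ambiguity, because the words evaluable and treatment period in the membership sentence can be read as importing the earlier condition.

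Second, SAP 3.3.2 says where applicable, so it does not promise every parameter for each drug. A reader might also infer that no listed parameter can be calculated, or that the tables themselves list the unsupported ones. Neither is right: entinostat Cmax, Tmax and AUC0-t are computable, and the tables are titles only. But the qualifier assigns no parameter to either drug, and a parameter table is still planned for pembrolizumab.

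Third, redacted exploratory text or the separate PK plan may define the reference agent or the PK methods. That is possible, and it is why reconciling the text is an acceptable alternative to deleting it. Neither source could add samples to the visible schedule.

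Fourth, the AUC ratios depend on assumptions that the SAP does not make. That is so: the wider timing range includes values below 1, so a consistent upward bias should not be inferred.

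**Conclusion.** The point holds as a minor defect. Applied literally, the primary PK analysis defined in SAP 3.2.5 has essentially no evaluable patients: there are 0 scheduled samples in a planned single-agent period, or one per patient in at most 15 patients if protocol 9.5 covers EMIC. The population for the PK tables is probably wider but not clearly worded.

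For entinostat, AUC0-inf, half-life and lambda_z lack an adequate basis; this rests on the sample counts and the assumed three-point convention. Cmax, Tmax and AUC0-t would be driven by sampling times; the size of the AUC0-t error rests on the simple model above. For pembrolizumab, no peak, AUC profile or terminal slope follows from the planned schedule, whatever model is assumed.

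A reader might take this to weaken the trial's safety or efficacy findings. It does not. No visible primary or secondary objective is a PK objective, the exposure-safety work sits with the population PK analysis in SAP 3.11, and only descriptive PK outputs are affected.

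**What to change.** - In SAP 3.2.5, remove the with-and-without and each-treatment-period conditions, or reconcile them with any redacted PK objective. Define the PK set per drug, for example at least one dose of that drug and at least one evaluable post-dose concentration with recorded dose and sample times.
- In SAP 3.3.2, remove the unsupported non-compartmental parameters and refer to SAP 3.11.
- Align Tables 14.2.2.1 and 14.2.2.2 with SAP 3.11, either by dropping them or by filling them from the population PK analysis. Summarise pembrolizumab troughs by cycle.
- State whether the sampling in protocol 9.5 applies to EMIC.

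The cost is SAP wording, table shells and one clarification of EMIC sampling. No new samples are needed.

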3.3 Analysis Variables

3.3.1 Efficacy Variables

Efficacy variables include:

- ORR (CR or PR) by irRECIST and RECIST 1.1
- CBR (CR, PR, or SD for at least 24 weeks) by irRECIST and RECIST 1.1
- PFS at 6 months by irRECIST and RECIST 1.1
- PFS as determined by irRECIST and RECIST 1.1
- OS
- DOR and TTR (in patients who achieve a best overall response of CR or PR)

3.3.2 Pharmacokinetic Variables

The following PK parameters for the plasma concentrations of entinostat or pembrolizumab will be calculated via non-compartmental methods and summarized, where applicable, using the WinNonlin™ software package (WinNonlin™ Phoenix, Version 6.3, Pharsight Corporation, Mountain View, CA).

Pharmacokinetic variables include:

- C_{max} , maximum plasma concentration
- T_{max} , time at which maximum plasma concentration was observed
- AUC_{0-t} , area under the plasma concentration-time curve from time zero to the last measurable concentration
- AUC_{0-inf} , area under the plasma concentration-time curve from time zero extrapolated to infinity
- $t_{1/2}$, elimination half-life
- λ_z , terminal elimination rate constant

All measurable plasma concentrations will be used for the analysis. For concentration values reported as no Results/not Reportable (NR), values will be treated as missing.

Values below the quantifiable limit (BQL) that occur prior to the first measurable concentration will be treated as zero. All other BQL values will be treated as missing. The mean plasma concentration over time by treatment and the individual subject plasma concentration versus time data will be plotted. Nominal times will be used for plotting the mean plasma concentrations over time by treatment. Actual sampling times will be used for the individual figures and for the non-compartmental analysis.

3.3.3 Safety Variables

Safety variables include:

- Determination of DLT, MTD and RP2D
- Incidence of TEAEs:

TEAEs are defined as any AE occurring or worsening in severity after the administration of study drug. TEAEs will be categorized as:

- Relationship to entinostat
- Relationship to pembrolizumab
- Severity/Grade according to National Cancer Institute Terminology Criteria for Adverse Events (NCI CTCAE) Version 4.03
- Action with respect to entinostat
- Action with respect to pembrolizumab
- Seriousness and outcome
- Change in chemistry and hematology parameters from baseline to minimum and maximum post-baseline values, average post-baseline value, and last post-baseline value
- Shifts in chemistry and hematology parameters from baseline to worst post-baseline in CTCAE toxicity grade
- Shifts in chemistry and hematology parameters outside the laboratory normal range from baseline to maximum increase and/or decrease, and last post-baseline value
- Change from baseline in vital signs and weight at each post-baseline time point
- Change from baseline in 12-lead ECG parameters at each post-baseline time point
- Change from baseline in ECOG at each post-baseline time point

3.3.4 Exploratory Variables

3.4 Disposition and Evaluability

3.4.1 Disposition

The number and percentage of patients who were enrolled, dosed, and withdrew prior to receiving a dose (including reasons for not completing dosing), the number of cycles on treatment, the reasons for discontinuation of each study treatment, the reason for discontinuation of the study, will be presented by dose cohort in Phase 1 and by tumor type and overall in Phase 2.

3.4.2 Protocol Deviations

Protocol deviations will be presented in a patient listing.

3.5 Demographics and Baseline Characteristics

3.5.1 Demographics

Demographics will be summarized by dose cohort for the Safety Analysis Set (Phase 1 only) and will be summarized by tumor type for the Safety Analysis Set (Phase 2). Frequency statistics will be presented for sex, race, ethnicity, age group, and ECOG performance status at baseline. Summary statistics will be presented for age, weight (kg), height (cm), and body surface area (m²).

Body surface area will be calculated using the Mosteller formula:

$$\text{Body surface area} = \sqrt{\frac{\text{height (cm)} \times \text{weight (kg)}}{3600}}$$

All demographic data will be presented in patient listings.

3.5.2 Cancer Disease History

The following baseline disease characteristics variables will be summarized (if available) **for each cohort in Phase 2** and the Safety Analysis Set:

- Time since initial diagnosis
- Disease stage at initial diagnosis
- Histopathological grade at initial diagnosis
- Time since diagnosis of advanced or metastatic cancer
- Metastatic sites

Disease history, including prior anti-cancer therapies (e.g. PD-1/PD-L1), surgeries, and radiotherapy, will be summarized by dose cohort and by tumor type for the Safety Analysis Set (Phase 1 only) and for the Safety Analysis Set (Phase 2 only), respectively. Frequency statistics will be presented for ECOG performance status, primary tumor location, and disease status at enrollment. Summary statistics will be

presented for months since diagnosis.

If the date of diagnosis is missing the day and/or month, the algorithm specified in Section 3.1.4 for incomplete dates will be used to determine the date and time since the study start.

All cancer disease history data will be presented in patient listings.

3.5.3 Medical History, Prior Medications, and Physical Exam

Data regarding medical history, prior medications, and clinically significant findings from the physical exam will be presented in patient listings for the Safety Analysis Set (Phase 1 only) and for the Safety Analysis Set (Phase 2).

3.6 Concomitant Medications

Any medication reported on the appropriate post treatment form (Concomitant Medications) will be considered concomitant.

All medications will be coded using the World Health Organization (WHO) Drug Dictionary (September 2016). The number and percentage of patients taking each concomitant medication will be presented by dose cohort (Phase 1) and tumor type (Phase 2) for the Safety Analysis Set. All medication data will be listed individually and summarized by anatomical therapeutic class and generic name.

3.7 Treatment Exposure

The total number of cycles started and the total number of cycles started by category (≥ 1 , ≥ 2 , ≥ 3 , so on) will be tabulated for each patient and summarized for each study phase. The cumulative dose of entinostat administered (in mg) will be calculated. These data will be further summarized by calculating the mean, standard deviation, median, and range of these values. The dose intensity = [total amount of actual dose of study drug / (prescribed dose per cycle * # of cycles)] * 100 will be calculated for all patients. Similar analyses will be performed for pembrolizumab administration (in mg/kg). The number and proportion of patients with one or more dosage modification (i.e., reduction or delay) of each study drug will be tabulated along with the reasons for dosage modification. The primary reason for study drug discontinuation will be tabulated in a

similar manner. All treatment exposure data will be presented in patient listings for the Safety Analysis Set.

